	
Any patient receiving rescue medication or parenteral hydration will be deemed a treatment failure.
 
Metoclopramide 0.3 mg/kg, maximum dose 10 mg, administered intravenously will be the default rescue medication. Oral metoclopramide or other antiemetics administered either intravenously or orally may be used at the investigator's discretion. However, patients are not to receive ondansetron or other 5-HT3 antagonists by any route for at least 24 hours after administration of study medication. The following 5-HT3 antagonists are available in the US: alosetron (Lotronex), dolasetron (Anzemet), granisetron (Sancuso and others), ondansetron (Zofran, Zuplenz and others), palonsetron (Aloxi).
 
Oral fluids will be administered as tolerated once a patient has not vomited for 30 minutes after dosing with study medication (second dose for those patients receiving 2 doses in the ED). Guidelines for administration of oral fluids are shown on page 20, section 4.4.1, of the protocol.
 
Patients tolerating oral fluids will be discharged once deemed stable by the attending physician but not prior to 4 hours after dosing. On discharge, patients will be given 3 additional doses of study medication to take once daily if necessary.
 
Patients who do not tolerate oral fluids may receive parenteral hydration. Data will be collected daily for up to 4 days following study initiation (until symptoms have resolved) to ascertain whether the patient had further vomiting, other sequelae of the acute gastroenteritis or required further medical care for the gastroenteritis. Data may be collected by entry by the patient or a caregiver into a web-based system or on paper, or by telephone contact daily from a study staff member. If during the follow-up period, symptoms progress or worsen or new symptoms develop, the patient may be asked to return for further evaluation. If by day 4 after discharge (i.e., the day after the last dose of study medication), the patient still notes gastroenteritis symptoms, he or she will be instructed to return for further evaluation.

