## Study Assessments

Day	1	1	1	2	3	4	5
Time, hours	-1 to 0	0	0-T	NA	NA	NA	NA
Baseline assessments a	X						
Study drug administration		X e		X f	X f	X f	
Observation b			X			X c	X c
Patient reported events c				X	X	X	X
Concomitant medications d	X	X	X	X	X	X	X
Adverse events		X	X	X	X	X	X

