cPrior to discharge, patients will be given diary pages to record their course after discharge. Patients will be contacted each day following treatment to a maximum of 4 days to determine whether they had further nausea and vomiting after leaving the emergency department, the occurrence and quality of bowel movements, including assessment using the Bristol stool scale (Appendix I), and the nature, occurrence and severity of other symptoms, whether they required further care for the acute gastroenteritis, and details regarding the continuation, if any, of the illness. If symptoms persist for 3 or more days after study entry, the patient is to be instructed to return for further evaluation.

dTo include all medications taken within 7 days prior to study entry, all treatments (including parenteral fluids) on the day of study entry, and all medication, including rescue medications, from the time of study entry through last follow-up.

ePatients are to receive the first dose of study medication within one hour of signing informed consent.

fPatients may take study medication daily for up to 3 days after study entry (maximum total of 4 doses, plus one additional if patient vomits within 15 minutes of first dose) if symptoms persist. Patients should stop taking study medication if symptoms have resolved, though they may resume study medication once daily if symptoms recur after discontinuation. Patients are not to take any remaining study medication after day 4. They will be given mailers to return any unused study medication.

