## 4. Study Design

### 4.1 Overview

Patients presenting to the emergency department who fulfill entry criteria will be asked to participate. A screening log will be kept listing all patients considered with reasons for patients not entering the study. Any patient whose information is reviewed in consideration for the study, even if not actually approached, is to be included in the screening log. The screening log will differentiate between those who are prescreened, i.e., who are reviewed but never progress to request for consent, from those who are screened, i.e., who are approached for consent, whether or not they actually sign consent or eventually participate in the study. Qualifying patients, once they have signed consent, will be stratified by age ( $\geq$  vs <age 18) and randomized 60:40 to RHB-102 or matching placebo. All patients will undergo laboratory testing and ECG, as specified below, once they have signed consent. However, only results of the pregnancy test (for women of childbearing potential) and a finger stick blood glucose (for patients with type 2 diabetes mellitus controlled by diet or oral medications) are required prior to treatment.

Patients will be started on oral fluids  $\geq$ 30 minutes after taking study medication (second dose for patients who receive 2 doses in ED) if they have not vomited during that period. Intravenous hydration should not be administered unless the patient has vomited or is clearly unable, after a reasonable period of time has elapsed since administration of study medication, to tolerate oral fluids.

At  $4\pm0.25$  hours after initial dosing, all patients are to have a repeat 12-lead ECG. Once stable, but not less than 4 hours after initial dosing, patients may be discharged from the emergency department. If a patient leaves the ED less than 4 hours after dosing, an ECG should be obtained if at all possible, even if the patient is leaving against protocol requirements.

On discharge, patients will be given an additional 3 doses of study medication to take at 24-hour intervals if nausea persists. Patients will be contacted daily for 4 days after discharge to determine their condition. Those patients who have persistent, worsening or recurrent nausea and/or vomiting during the follow-up period may be asked to come in for follow-up assessment by study personnel.

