#### 4.4.2 Serotonin syndrome

5-HT3 antagonists, including ondansetron, have been associated with serotonin syndrome. When given as a single agent, ondansetron overdose has been associated with serotonin syndrome. However, most reports of serotonin syndrome have been associated with concomitant use of serotonergic drugs (e.g., selective serotonin reuptake inhibitors (SSRIs), serotonin and norepinephrine reuptake inhibitors (SNRIs), monoamine oxidase inhibitors, mirtazapine, fentanyl, lithium, tramadol, and intravenous methylene blue). Some of the reported cases were fatal.

Symptoms associated with serotonin syndrome may include the following combination of signs and symptoms: mental status changes (e.g., agitation, hallucinations, delirium, and coma), autonomic instability (e.g., tachycardia, labile blood pressure, dizziness, diaphoresis, flushing, hyperthermia), neuromuscular symptoms (e.g., tremor, rigidity, myoclonus, hyperreflexia, incoordination), seizures, with or without gastrointestinal symptoms (e.g., nausea, vomiting, diarrhea). Patients should be warned about and monitored for the emergence of serotonin syndrome, especially with concomitant use of other serotonergic drugs. If symptoms of serotonin syndrome occur, discontinue RHB-102 and initiate supportive treatment.

All medications taken in the 7 days prior to study entry and from the time the patient arrives in the emergency room until he or she completes the study will be recorded in the case report form (CRF).

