#### 5.2.3 Procedures after discharge from emergency department:

Any patient who has a post-dosing ECG showing QTc>500 msec must have a follow-up ECG within 72 hours of initial dosing showing resolution of the QTc prolongation. This may be performed on an inpatient or outpatient basis at the investigator's discretion. If the QTc does not decrease below 500 msec during initial follow-up, the medical monitor must be contacted to discuss further follow-up.

If a patient vomits from 30 minutes after taking the first dose of study medication until 24 hours after the first dose of study medication or requires rescue antiemetic or parenteral hydration during that period, even without vomiting, he or she will be considered a treatment failure. In that case, the only post-emergency department follow-up will be a call 72-96 hours after discharge from the emergency department to ascertain whether the patient's symptoms have

resolved, whether any adverse events occurred, and whether the patient required further medical follow-up, either in an emergency department or other medical facility.

Prior to discharge, patients who are treatment successes (i.e., no vomiting, no rescue medication and no parenteral hydration while in emergency department) will be given a diary card to record:

- all episodes of vomiting and bowel movements, with description of each bowel movement
- severity of nausea (on a 5-point Likert scale) three times a day: before breakfast or the time at which the patient usually eats breakfast, between 1:00-2:00 pm, and at bedtime
- any symptoms the patient may have related to gastroenteritis, such as chills, fever, abdominal pain
- adverse events
- medications taken, either for gastroenteritis (study medication and others) or other conditions

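### Protocol 5.2.3 cuts post-ED data collection for 24-hour failures, against the assessment schedule, so secondary symptom analyses labelled ITT may rest mainly on treatment successes

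*Protocol*

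**What the plan says.** Protocol 5.2.3 treats a patient who fails between 30 minutes and 24 hours after the first dose as a special case: "the only post-emergency department follow-up will be a call 72-96 hours after discharge from the emergency department". That call covers whether symptoms have resolved, adverse events and further medical care. The same section says that patients with no vomiting, rescue or parenteral hydration "while in emergency department) will be given a diary card to record" vomiting, bowel movements, nausea three times a day, other symptoms, adverse events and medications.

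Other places describe follow-up without excluding failures:

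- **Study Assessments table:** the row "Patient reported events" is marked on days 2 to 5. Its note c reads "Prior to discharge, patients will be given diary pages to record their course after discharge" and adds contact each day up to 4 days.
- **Synopsis, Methodology:** "Data will be collected daily for up to 4 days following study initiation (until symptoms have resolved". The sentence before it concerns patients who may receive parenteral hydration, who are failures by definition.
- **Protocol 4.1 and SAP 3.1:** "Patients will be contacted daily for 4 days after discharge to determine their condition".
- **Protocol 4.5:** patients or caregivers keep a diary on each of 4 days, with daily contact as the alternative.
- **Protocol 5.2.3, later paragraph:** contact at least daily for 4 days, based on the diary card. This could cover all patients or card holders only.

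On analysis, SAP 9.3 uses the ITT population for all secondary and tertiary endpoints. SAP 8 and 9.2 impute drop-outs and unknown outcomes as failures for the primary analysis. The other rule in SAP 8 concerns diary dates, not outcomes.

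**The concern.** Protocol 5.2.3 lets the primary outcome decide how much later data a patient contributes. Because the design expects placebo patients to fail twice as often as RHB-102 patients, the loss would be unequal by arm.

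The endpoints exposed are post-ED severity of nausea, diarrhea by either scale, other gastroenteritis symptoms and days to normal activities. A comparison of available data on these would be mainly one of treatment successes in each arm. That group is formed after randomization, and calling the result ITT would mislead. For days to normal activities, which fits the log-rank and Kaplan-Meier methods of SAP 9.3, failures could stay in the set, but their censoring would be tied to having failed.

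**Working it through.** **1. The plan's own figure.** Protocol 7.1 assumes 40% failure on placebo and 20% on RHB-102, two-sided 0.01, 90% power and 60:40 allocation, and gives 128 + 192 = 320. With k = 1.5, pooled rate (0.40 + 1.5 × 0.20)/2.5 = 0.28 and no continuity correction:

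n(placebo) = [2.576 × √(0.28 × 0.72 × (1 + 1/1.5)) + 1.282 × √(0.40 × 0.60 + 0.20 × 0.80/1.5)]² / 0.20² = 126.3, rounded up to 127.

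This gives 127 + 191 = 318; power at 128 + 192 is 90.4%. The stated size is reproduced. Its failure rates are used below only to size the affected group.

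**2. Patients limited to one call under 5.2.3.**

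| | Placebo | RHB-102 | Total |
|---|---|---|---|
| 24-hour failures | 0.40 × 128 = 51.2 | 0.20 × 192 = 38.4 | 89.6/320 = 28% |
| 24-hour successes | 76.8 | 153.6 | 230.4 |

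If placebo failure were 30% or 50%, with the same halving on RHB-102, the total would be 67.2/320 = 21% or 112/320 = 35%. These are upper bounds on lost data, because a patient who leaves the ED as a success and fails at home already holds a diary card. The protocol does not say whether that diary is then collected. If half of the failures in each arm occur in the ED (assumption), 25.6 placebo and 19.2 RHB-102 patients never receive a card.

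**3. Effect on a symptom comparison.** Assume a later symptom in 60% of failures and 20% of successes, the same in both arms.

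- True rates: placebo 0.4 × 0.6 + 0.6 × 0.2 = 36%; RHB-102 0.2 × 0.6 + 0.8 × 0.2 = 28%. The difference is 8 points.
- All failures in the ED, so only successes are observed: 20% against 20%, difference 0.
- Half of failures in the ED, other diaries collected: (0.2 × 0.6 + 0.6 × 0.2)/0.8 = 30.0% against (0.1 × 0.6 + 0.8 × 0.2)/0.9 = 24.4%, difference 5.6 points.

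Unequal mixes can also create a difference. Suppose 60% would succeed on either arm (later nausea 10%), 20% would fail only on placebo (later nausea 20–40% on either arm) and 20% would fail on both. Suppose too that all failures are in the ED and drug has no effect on later nausea. RHB-102 successes then show (0.06 + 0.2 × 0.2)/0.8 = 12.5% to (0.06 + 0.2 × 0.4)/0.8 = 17.5%, against 10% in placebo successes, although the true difference is 0.

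**4. Days to normal activities.** Assume 80% of successes and 40–70% of failures resume by day 4. The true RHB-102 advantage is 0.2 × (0.80 − 0.40) = 8 points down to 0.2 × (0.80 − 0.70) = 2 points. With all failures in the ED, the result turns on when they are censored, which no document states:

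- Censored before any event: 80% against 80%, difference 0.
- Kept event-free at risk and censored at the 72–96 h call: 0.8 × 0.80 = 64% against 0.6 × 0.80 = 48%, difference 16 points.

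The same missing data can therefore erase the effect or more than double it.

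**The case against.** The best defence is that 5.2.3 is the detailed rule and states its exception expressly, while the texts set against it are summaries. Those summaries drop failure exceptions elsewhere: the synopsis and Protocol 4.1 give take-home doses to patients in general, although Protocol 4.5 and 8 and SAP 3.1 withhold them from ED failures. In SAP 3.1 the contact sentence directly follows one limited to patients who are not failures, and the diary paragraph of 4.5 follows one about patients without ED failure. This stands in part: the synopsis, 4.1, 4.5 and SAP 3.1 are in tension with 5.2.3 rather than in plain conflict. It does not dispose of note c and its table row, which set out the diary and daily contact with no exception. If 5.2.3 governs after all, the loss of data is built in and the ITT label is still wrong.

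SAP 9.3 also refers other proportion endpoints to the same test as in 9.2, which might be argued to bring the failure imputation with it. The wording names a test, and the argument could not reach ordinal or time-to-event endpoints.

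The reach is limited, and this stands. The decision rule in SAP 5.2 concerns the primary endpoint only. The following are unaffected or largely captured:

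- the primary endpoint in patients classed as failures, and treatment success through 4 days, since a 24-hour failure is already a 4-day failure;
- time to discharge, and the supplemental time to no nausea, which uses hourly ED data;
- ED return and hospitalization, because the single call asks about further care;
- rescue use, because note d requires "all medication, including rescue medications, from the time of study entry through last follow-up" and Protocol 4.4.2 covers medications "from the time the patient arrives in the emergency room until he or she completes the study".

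**Conclusion.** The conflict between 5.2.3 and note c with its table row is in the current text. Whether data were lost is not shown, because the documents do not say which rule sites followed. If 5.2.3 was followed, up to 51 of 128 placebo and 38 of 192 RHB-102 patients (about 90 of 320, at the planned rates) lack daily post-ED data because they failed, most completely those who failed in the ED. The affected secondary comparisons would not be ITT in substance, and the SAP has no clear rule for the gap. This is a cheap improvement to secondary results and leaves the primary test alone.

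Three stronger inferences are not supported.

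- **That the bias mostly runs against RHB-102.** The examples give dilution, reversal or inflation depending on assumed rates and an unstated censoring time.
- **That counting missing vomiting status as vomiting (Supplemental SAP 12) inflates the vomiting difference.** Supplemental SAP 11 codes failures by IV fluid or rescue alone as patients who did not vomit, apart from drop-outs and unevaluable patients, and the listing in section 15 also separates them. Counting them as non-vomiters could understate the effect. If 20% or 50% of failures are of this kind, and 50% or 25% of them vomit later, the true difference is 0.2 × (1 − 0.2 × 0.5) = 18 or 0.2 × (1 − 0.5 × 0.75) = 12.5 points, against 0.2 × 0.8 = 16 or 0.2 × 0.5 = 10 observed.
- **That adverse-event rates are distorted by a stated amount.** The documents give no base rate, and the single call still asks about adverse events.

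**What to change.** **Protocol text.** Reconcile 5.2.3 with the synopsis, the Study Assessments table and note c, 4.1, 4.5 and SAP 3.1. Every dosed patient should have the same diary and daily data-collection contacts for 4 days whatever the outcome, including the question on normal activities. A diary already held should still be collected after a failure. This concerns data collection only.

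**Data already collected under 5.2.3.**

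1. Label post-ED symptom summaries as patients with diary follow-up, not ITT.
2. Report the number with data by arm, day and 24-hour outcome. This would also show whether the loss occurred.
3. State the censoring time used for failures in the normal-activities analysis, and the number so censored by arm.
4. In the supplemental vomiting analysis, report by arm how many patients counted as vomiting were observed to vomit and how many come from the missing-data rule.

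Supplemental SAP 3 gives June 3, 2017 as the date of unblinding, so any imputation for failures can only be a post hoc sensitivity analysis.

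**Cost.** For this trial, labels and a few count tables. The wording change can now only clarify the record or serve a later study. There it would add up to about 90 patients to a diary and contact process that already exists, and some of those patients may refuse.

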### 4.2 Study Drug Administration

After results of the pregnancy test and/or blood glucose (when required) are obtained and determined to be negative/within acceptable limits and the patient is randomized, the investigator or a designate will administer the first dose of study medication under observation. If the patient vomits within 15 minutes, regardless of whether pill fragments are seen, a second dose of study medication will be administered by the investigator or a designate. If a patient retches but does not actually vomit any gastric contents, no second dose will be administered. If a patient vomits again, regardless of how long after the second dose of study medication, no further study medication will be administered.

Patients vomiting  $\geq$ 30 minutes after the first dose of study medication may receive rescue antiemetics, either parenterally or orally. In addition, patients with

severe nausea  $\geq$ 30 minutes after dosing with study medication and which in the investigator's opinion requires treatment may receive rescue medication. Metoclopramide 0.3 mg/kg, maximum dose 10 mg, administered intravenously will be the default rescue medication. Oral metoclopramide or other antiemetics administered either intravenously or orally may be used at the investigator's discretion. **However, patients are not to receive ondansetron or other 5-HT3 antagonists by any route for at least 24 hours after administration of study medication either in the ED or after discharge.** The following 5-HT3 antagonists are available in the US: alosetron (Lotronex), dolasetron (Anzemet), granisetron (Sancuso and others), ondansetron (Zofran, Zuplenz and others), palonsetron (Aloxi).

Oral fluids will be administered as tolerated once a patient has not vomited for 30 minutes after dosing with study medication (second dose for those patients receiving 2 doses in the ED). Only patients who do not tolerate oral fluids after an adequate attempt at oral hydration may receive parenteral hydration. Patients are not to receive intravenous hydration until it is clear to the treating physician that the patient is clearly in need of parenteral hydration.

Patients tolerating oral fluids will be discharged once deemed stable by the attending physician but not prior to 4 hours after dosing and repeat ECG.

Patients who do not tolerate oral fluids will receive parenteral hydration.

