## 7. Data Analysis and Statistical Considerations

### 7.1 Sample Size Considerations

The primary endpoint is a composite of the following three parameters from 30 minutes until 24 hours after the first dose of study medication:

- absence of vomiting
- no use of rescue medication, and
- no intravenous hydration

If all of the above three criteria are fulfilled, the patient is considered a treatment success for the primary analysis. If one or more of the above three criteria are not fulfilled, i.e., the patient either experiences vomiting, receives rescue medication or receives intravenous hydration from 30 minutes through 24 hours after the first dose of study medication, the patient is considered a treatment failure.

It is expected that approximately 40% of the placebo group will fail treatment during the 24 hours after initial dosing and that RHB-102 will reduce the incidence of treatment failure by approximately 50%, i.e., to an incidence of 20% in the active treatment group. Patients will be stratified by age (<18,  $\geq$ 18 years of age) and randomized 60:40 to active versus placebo. To demonstrate a statistically significant decrease in the incidence of vomiting with a 2-tailed p-value=0.01 and power=90%, 320 patients will be entered into the study, 192 randomized to RHB-102 and 128 to placebo.

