8. HANDLING OF MISSING VALUES

Every effort will be made to collect all vomiting-related information. In the ED, patients will be under observation, complete efficacy data is expected. Rare cases may occur in which a patient leaves the ED before any observations can be made. In addition, some patients may not report events between the time they leave the ED and 24 hours after first dose of study medication. It is expected that >90% of patients will provide data until at least 24 hours after initial dosing. Patients who drop out of the study and patients who have unknown primary endpoint will be imputed as failures/non-responders for the primary analysis.

Diary dates will be imputed based on nominal date. For example, a subject's first dose in ED is 18May2017, his/her ER day diary date will be 18May2017 and his/her Day 1 diary date will be 19May2017.

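### Protocol 5.2.3 ties the diary card to no vomiting at any time in the ED, while the primary endpoint counts vomiting only from 30 minutes after the first dose

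*Protocol*

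**What the plan says.** The primary endpoint has a delayed start. Protocol 7.1: "The primary endpoint is a composite of the following three parameters from 30 minutes until 24 hours after the first dose of study medication". A patient is a failure if "the patient either experiences vomiting, receives rescue medication or receives intravenous hydration from 30 minutes through 24 hours after the first dose". SAP 7.1 and Protocol 5.2.2 use the same 30-minute start.

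The design expects some vomiting before that point. Protocol 4.2: "If the patient vomits within 15 minutes, regardless of whether pill fragments are seen, a second dose of study medication will be administered". Every redosed patient has therefore vomited in the ED.

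Protocol 5.2.3 then sets post-discharge follow-up in two consecutive paragraphs. The first defines failure with the endpoint's window ("If a patient vomits from 30 minutes after taking the first dose of study medication until 24 hours after the first dose of study medication") and gives failures a single call at 72-96 hours. The second concerns successes: "patients who are treatment successes (i.e., no vomiting, no rescue medication and no parenteral hydration while in emergency department) will be given a diary card". Its parenthesis has no time limit. Later in the same section, patients are to be contacted at least daily for 4 days, and the diary card is made the basis of the data collected in those calls.

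Elsewhere the diary has no such condition. Note c to the Study Assessments table: "Prior to discharge, patients will be given diary pages to record their course after discharge". Protocol 4.5 has patients or caregivers keep a diary for 4 days or be contacted daily. The Synopsis (Methodology) allows web, paper or daily telephone collection.

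On missing outcomes, SAP 8 adds to dropouts that "patients who have unknown primary endpoint will be imputed as failures/non-responders for the primary analysis".

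**The concern.** A patient whose only ED vomiting came in the first 30 minutes fits neither of the two paragraphs in 5.2.3. The patient has not failed, so the single call does not apply. The patient also does not meet that section's description of a success, so the card is not issued.

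Discharge is allowed from 4 hours after dosing, so for a patient discharged near that time most of the 24-hour window lies after discharge and has to be reported from home. A site that follows the wording literally removes the main record of that period for the very patients whose early vomiting the endpoint is built to disregard. If the outcome then cannot be established, the primary analysis scores a failure. Would-be successes lost in this way would shrink the difference between arms. If early vomiting were more common in one arm, they would also bias it.

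**Working it through.** **Side by side.** Consider a patient who vomits once at 10 minutes, is redosed, and has no later event in the ED.

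| Text | Status of this patient |
|---|---|
| Protocol 7.1, SAP 7.1 (endpoint) | Not a failure; success still possible |
| Protocol 5.2.2; 5.2.3, failure paragraph | Not a failure; single-call rule does not apply |
| Protocol 5.2.3, diary-card paragraph | Not a success as glossed; no card |
| Study Assessments note c; Protocol 4.5 | Diary, or daily contact under 4.5 |
| Protocol 5.2.3, later text; Protocol 4.1 | Daily contact for 4 days |

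The diary-card paragraph is the one that conflicts with all the others.

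**Plan's own sample size.** Inputs from Protocol 7.1: failure 40% on placebo (n = 128) and 20% on RHB-102 (n = 192), two-sided 0.01, power 90%. The pooled normal formula for two proportions, without continuity correction, requires 127 + 191 = 318, against 320 stated.

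Power = Φ[(p0 − p1 − z·SE0)/SE1], where
- pooled p = (128 × 0.40 + 192 × 0.20)/320 = 0.28
- SE0 = √[0.28 × 0.72 × (1/128 + 1/192)] = 0.0512
- SE1 = √[0.40 × 0.60/128 + 0.20 × 0.80/192] = 0.0520

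At 0.01 (z = 2.576) this gives Φ(1.307) = 90.4%, which reproduces the plan. At 0.05 (z = 1.960), the level used for the test in Protocol 7.4.1 and SAP 9.2, it gives Φ(1.914) = 97.2%.

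**Effect of unscored early vomiters.** Let a share f of each arm be early vomiters whose outcome is unknown and imputed as failure. Assume they would otherwise have failed at the same rate as everyone else. The failure rates become p0 = 0.40 + 0.60f and p1 = 0.20 + 0.80f.

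The only documented anchor for f is SAP 7.1. Of 28 patients with incomplete information, 17 lacked an ER day diary and all 17 were classed as successes from other follow-up data. Of the other 11, 4 were classed as successes, 1 as a failure and 6 as unknown (17 + 11 = 28; 4 + 1 + 6 = 11). Taking all 6 as early vomiters gives f = 6/320 = 1.9% of the planned total.

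| f | Placebo v RHB-102 failure | Difference (points) | Power at 0.05 | Power at 0.01 |
|---|---|---|---|---|
| 0 | 40.0% v 20.0% | 20.0 | 97.2% | 90.4% |
| 1.9% (all 6 unknowns) | 41.1% v 21.5% | 19.6 | 96.4% | 88.2% |
| 5% (assumed) | 43.0% v 24.0% | 19.0 | 94.6% | 84.1% |
| 10% (assumed) | 46.0% v 28.0% | 18.0 | 91.0% | 76.6% |

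The last two rows only show sensitivity. The documents give no rate of vomiting in the first 30 minutes, and these rows require every such patient to end with an unknown outcome.

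**The case against.** The strongest reply is that one loose parenthesis does not withhold follow-up. Note c, Protocol 4.5 and the Synopsis supply a diary or telephone collection without the condition. Daily contact in Protocol 4.1 and 5.2.3 is not limited by ED vomiting, and the only stated exception, the single call, uses the 30-minute definition. A reader might infer from 5.2.3 that early vomiters are simply lost to follow-up. The documents do not support that. What stands against the reply is that 5.2.3 is the section a site would consult for post-discharge procedures, that it makes the card the basis of the calls, and that conflicting text elsewhere does not repair it.

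A reader might also infer that a missing diary means an imputed failure. SAP 7.1 shows otherwise: all 17 patients without an ER day diary became successes. That evidence has limits. Those patients were treated under amendment 1 or 2, when the primary endpoint was success at ED discharge. They were resolved by a case review added in SAP versions 3.0 and 4.0, not by a standing rule for missing diaries. The SAP does not say whether any of the 28 were early vomiters.

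Finally, SAP 9.2 already plans an analysis with all unknowns and dropouts as responders, and a worst case with failures on active and responders on placebo. Section 15 of the supplemental SAP lists the outcomes of redosed patients. Both help. Neither shows how patients who vomited at 15-30 minutes, and so were not redosed, were followed and scored.

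**Conclusion.** The inconsistency is real and touches data collection for the primary endpoint, but its likely effect is small. If all 6 remaining unknowns were early vomiters, spread over the arms in proportion to size and otherwise failing at the planned rates, the difference would fall from 20.0 to 19.6 points and power at 0.05 from 97.2% to 96.4%. The 6 are the unknowns left after review; section 11 of the supplemental SAP codes early dropouts separately, but lacking a diary card is not the same as dropping out.

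Two stronger conclusions should not be drawn. One is that redosed patients count as primary successes. They only remain eligible, and they fail if they vomit, receive rescue medication or receive intravenous hydration from 30 minutes to 24 hours. The other is that the treatment comparison is materially weakened or biased. Larger power losses need an early-vomiting rate that the documents do not give, and nothing in them shows a difference between arms or its direction.

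**What to change.** In Protocol 5.2.3, define diary eligibility by the endpoint's own window: no vomiting, rescue medication or parenteral hydration from 30 minutes after the first dose up to ED discharge. Alternatively, give the diary to every patient who has not failed. Either version agrees with note c, Protocol 4.5 and the daily-contact text. State explicitly that vomiting before 30 minutes, including vomiting that led to a second dose, does not remove a patient from diary follow-up.

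In the analysis, tabulate by arm the 24-hour outcome (success, failure, unknown) of patients whose only vomiting was in the first 30 minutes. This extends the listing in section 15 of the supplemental SAP, which covers only redosed patients.

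The cost is one sentence, some additional diary cards in an existing process, and one table. The supplemental SAP dates unblinding to 3 June 2017, so for these data only the table can still help, and it would be descriptive. The wording change serves any later use of the protocol.

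Separately, the conditions for further study medication after ED vomiting differ between Protocol 4.5 and 4.6 (vomiting in the ED, with no 30-minute limit) and Protocol 8 and SAP 3.1 (not having failed). These sections must be reconciled.
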